8.2.1 Reasons for Removal From Invasive Procedures

Reasons for removal from the invasive procedures include any of the following:

- Decision by Sponsor
- Lost to follow-up
- Death
- Ineligibility determined
- Protocol deviation
- Non-compliance
- Adverse event
- Subject request
- Requirement for alternative therapy not allowed by protocol
- Pregnancy

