7.1.7 Excluded Treatments, Medical Devices, and/or Procedures During Study Period

The following treatments are not permitted during the study:

- Non-study investigational therapies
- Any lipid lowering therapies not taken at the time of screening and enrollment

Please contact the Amgen medical monitor or designee if any of these therapies should be initiated during the study. Note that a change in background lipid-lowering therapy (including statins), does not necessarily require ending investigational product.

The following treatments are not recommended in subjects treated with statins metabolized by cytochrome P450 (CYP) 3A4 (eg, simvastatin or atorvastatin) because of their potential impact on metabolism of certain statins:

- Medications or foods that are known potent inhibitors of CYP 3A4 (eg, itraconazole, ketoconazole, and other antifungal azoles, macrolide antibiotics erythromycin, clarithromycin, and the ketolide antibiotic telithromycin, human immunodeficiency virus or hepatitis C virus (HCV) protease inhibitors, antidepressant nefazodone and grapefruit juice in large quantities (> 1 quart daily [approximately 1 L]) should not be used during the study.

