8.1 Discontinuation of Study Treatment

Subjects (or a legally acceptable representative) can decline to continue receiving investigational product and/or other protocol-required therapies or procedures at any time during the study but continue participation in the study. If this occurs, the investigator is to discuss with the subject the appropriate processes for discontinuation from investigational product or other protocol-required therapies and must discuss with the subject the possibilities for continuation of the Schedule of Activities (see [Table 2-1](#)) including different options of follow-up (eg, in person, by phone/mail, through family/friends, in correspondence/communication with other treating physicians, from the review of medical records) and collection of data, including endpoints, adverse events,

and device-related events, as applicable and must document this decision in the subject's medical records. Subjects who have discontinued investigational product and/or other protocol-required therapies or procedures should not be automatically removed from the study. Whenever safe and feasible, it is imperative that subjects remain on-study to ensure safety surveillance and/or collection of outcome data.

Subjects may be eligible for continued treatment with Amgen investigational product(s) and/or other protocol-required therapies by a separate protocol or as provided for by the local country's regulatory mechanism, based on parameters consistent with [Appendix 3](#).

Reasons for removal from protocol-required investigational product(s) or procedural assessments include any of the following:

- Decision by Sponsor
- Lost to follow-up
- Death
- Ineligibility determined
- Protocol deviation
- Non-compliance
- Adverse event
- Subject request
- Requirement for alternative therapy not allowed by protocol
- Pregnancy

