9.1.2 Treatment Period

Visits will occur per the Schedule of Activities ([Table 2-1](#)). On-study visits may be completed within 50 weeks and must occur within ± 7 days of their specified date (with the exception of the week 50 OCT and IVUS). The date of the first dose of investigational product is defined as day 1. All subsequent doses and study visits will be scheduled based on the day 1 date. Administration of investigational product is to be administered last during each visit that it is required.

Approved

Before each study visit where fasting lipid samples are obtained, subjects must be fasting overnight. If the subject is not fasting for the day 1 visit, no visit procedures are performed and the visit should be rescheduled within the applicable protocol windows. If subject is not fasting after day 1, all procedures except fasting labs and investigational product administration, if applicable, will be performed and another visit should be scheduled, within the visit window if possible, for fasting labs and investigational product administration.

The study includes collection of biomarker samples.

Final, follow-up OCT and IVUS should take place 50 ± 2 weeks (ie, 48 to 52 weeks) after initial baseline image acquisition. It is critical that the follow-up OCT and IVUS be obtained for all subjects, regardless of whether they discontinued study drug prematurely or are outside the 50 ± 2 weeks window.

9.1.2.1 Clinically Indicated Catherization Prior to Week 40

For subjects requiring coronary angiography prior to week 40, the final OCT and IVUS examination should not be performed in these subjects at the time of clinically indicated catherization. Subjects will remain on study drug and complete all required visits and procedures, including the week 50 OCT and IVUS.

For subjects requiring coronary angiography with intervention of the targeted vessel prior to week 40, these subjects will continue investigational product and complete all study visits and procedures with the exception of the week 50 OCT and IVUS.

9.1.2.2 Clinically Indicated Catherization at Week 40 Prior to Week 50

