10.1 Sample Size Determination

The planned total sample size is 150 subjects (75 randomized to evolocumab 420 mg SC QM and 75 randomized to placebo SC QM). This sample size will provide sufficient power (90%) to determine whether there is a treatment effect of evolocumab relative to placebo in the primary endpoint.

Approved

The assumptions in the sample size calculation are based on a linear regression meta-analysis of 7 historical trials (Dai et al, 2017; Hou et al, 2016; Kataoka et al, 2014; Komukai et al, 2014; Nishio et al, 2014; Hattori et al, 2012; Takarada et al, 2009) weighted by sample sizes.

The analysis result indicates that every 1 mg/dL reduction in LDL-C is estimated to be associated with 1.4785 μm increase in FCT in 12-month follow-up. Assuming a 50 mg/dL reduction in LDL-C, the predicted mean increase (95% CI) in FCT from the meta-analysis was 73.92 (50.97, 96.88) μm . For this study, the assumed treatment effect is at least 50.97 μm increase in FCT, which is approximated from the lower bound 95% CI of the expected change in FCT from the regression model, based on a conservative assumption of 50 mg/dL reduction in LDL-C from baseline to week 50.

The SD of FCT measurement at baseline or at the end of various length of follow-up was reported in a wide range (10.6 to 124 μm) based on 15 to 134 subjects per arm in the historical trials. The SD of change in FCT was only reported in 2 of the 7 trials, ranging from 22 to 86 μm . The assumed common SD for this study is 86 μm to be conservative.

Assuming 1 out of 6 subjects will not complete both baseline and week 50 OCT assessments, and therefore be excluded in the primary analysis, the sample size of 150 subjects will provide approximately 125 subjects in the primary analysis to ensure 90% power to test the study hypothesis.

The sample size calculation was performed using a 2-sided t-test with a 0.05 significance level. The sample size calculation was derived using East[®] software (version 6.4).

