
 To evaluate the effects of evolocumab on lipid parameters in subjects with NSTEMI-ACS who are taking maximally tolerated statin therapy To evaluate the effects of evolocumab on features of coronary plaques in subjects with NSTEMI-ACS who are taking maximally tolerated statin therapy using different imaging techniques. 	
 Absolute and percent changes in lipid parameters by visit from baseline. Absolute change in number of microchannels in matched segments of all lesions assessed in an individual subject as determined by OCT from baseline to week 50. Absolute change in macrophage composition in matched segments of all lesions assessed in an individual subject as determined by OCT from baseline to week 50. Absolute changes in lipid content in matched segments of all lesions assessed in an individual subject as determined by IVUS from baseline to week 50.

Page 2 of 2

The primary estimand consists of:

- The target population, which is the adult subjects with NSTEMI-ACS who are taking maximally tolerated statin therapy with or without additional lipid-modifying medication.
- The primary variable, which is the absolute change in minimum FCT in a matched segment of artery as determined by OCT from baseline to week 50.
- The summary measure, which is the mean treatment difference of the primary variable means between evolocumab and placebo.
- The intercurrent events, all randomized subjects who receive at least 1 dose of investigational product regardless of adherence to treatment or commencing commercial proprotein convertase subtilisin/kexin type 9 (PCSK9) inhibitors.

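### The protocol lets the week 50 OCT be omitted for non-compliance or a disallowed therapy, against its own imaging rule and estimand, and no planned analysis departs from missing at random

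*Protocol*

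**What the plan says.** **Reasons for not scanning.** Protocol Section 8.2.1 begins "Reasons for removal from the invasive procedures include any of the following". Its list includes ineligibility, protocol deviation, non-compliance and "Requirement for alternative therapy not allowed by protocol". Section 8.1 carries the same ten items, and its lead-in covers procedural assessments as well as investigational product. The opening of Section 8 gives both lists force: the investigator or the sponsor may withdraw a subject from protocol procedures for those reasons.

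**The imaging rule.** Protocol Section 9.1.2 states: "It is critical that the follow-up OCT and IVUS be obtained for all subjects, regardless of whether they discontinued study drug prematurely". The synopsis says the same. Section 7.4.1.1 keeps subjects who cannot tolerate the drug in all other procedures. Section 9.1.2.1 excuses the week 50 scan in one named case, intervention on the targeted vessel before week 40.

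**The estimand.** Protocol Section 4.1 includes every randomized, dosed subject whatever their adherence. SAP Section 2.1 adds "or commencing commercial proprotein convertase subtilisin/kexin type 9 (PCSK9) inhibitors".

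**Disallowed therapy.** Protocol Section 7.1.7 bars lipid-lowering drugs not already in use at screening and enrollment, but notes that a change in background lipid therapy "does not necessarily require ending investigational product".

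**Missing scans.** SAP Section 9.5.1 keeps subjects without a follow-up value in the full analysis set by multiple imputation. The imputation model holds treatment group, stratification factor, baseline LDL-C, baseline minimum FCT and age.

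**The concern.** In the Schedule of Activities the only catheter-based study procedure after randomization is the final OCT/IVUS. Section 8.2.1 therefore decides, in practice, when the primary endpoint may go uncollected. Two of its reasons match events that the estimand says to count: non-adherence and, in the SAP, starting a commercial PCSK9 inhibitor, which Section 7.1.7 makes a disallowed therapy.

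A site could follow Section 8.2.1 and skip the scan, or follow Section 9.1.2 and obtain it, and nothing says which section prevails. If the scan is skipped, the imputation model has no term for adherence, new lipid therapy or on-treatment LDL-C. An evolocumab subject who stopped injecting is then imputed like any other evolocumab subject, and a placebo subject who started a PCSK9 inhibitor like any other placebo subject. What is at stake is whether the primary result still estimates the stated treatment-policy effect.

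**Working it through.** **1. The plan's own figure.** Protocol Section 10.1 gives: "The sample size calculation was performed using a 2-sided t-test with a 0.05 significance level"; "the assumed treatment effect is at least 50.97" µm; common SD 86 µm; one subject in six without both scans, so 150 × 5/6 = 125 analysed. The claim is "This sample size will provide sufficient power (90%) to determine whether there is a treatment effect of evolocumab relative to placebo". With 62 + 63 subjects the noncentrality is 50.97 / (86 × √(1/62 + 1/63)) = 3.31, and the two-sided t-test has 90.8% power. The smallest equal group size reaching 90% is 61 per arm (90.1%). The stated figure reproduces. With all 75 + 75 scanned, power would be 95.0%.

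**2. Bias formula.** Let Δ be the effect among scanned subjects. Let m_E and m_P be the shares of each arm left unscanned because of these events. Let s_E and s_P be how far those subjects' mean change would differ from the rest of their own arm. Imputation under missing at random targets Δ, while the treatment-policy effect is Δ + m_E·s_E − m_P·s_P. So

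bias = m_P·s_P − m_E·s_E.

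The sign depends on four quantities that the documents do not give.

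**3. Illustrations.** Assume Δ = 50.97 µm, the planning value, and that no affected subject is scanned.

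*Both upward mechanisms, share q in each arm, each subject shifting by a fraction f of the effect:* truth = 50.97 × (1 − 2qf).
- q = 5%, f = 0.5: 50.97 × 0.95 = 48.4 µm, bias +2.5 µm
- q = 10%, f = 0.5: 50.97 × 0.90 = 45.9 µm, bias +5.1 µm
- q = 10%, f = 1: 50.97 × 0.80 = 40.8 µm, bias +10.2 µm

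*Range of signs, full-effect shifts, from 2% of an arm up to the planned one in six:*

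| Who differs from the rest of their arm | Bias at 2% | Bias at 16.7% | Truth at 16.7% |
|---|---|---|---|
| Evolocumab removals lose all benefit | +1.0 | +8.5 | 42.5 |
| The same, and placebo removals gain the full effect | +2.0 | +17.0 | 34.0 |
| Both arms' removals shift equally | 0 | 0 | 50.97 |
| Only placebo removals differ, faring worse by 50.97 µm | −1.0 | −8.5 | 59.5 |

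**4. Simulation check.** Settings: 75 per arm, one-sixth removed, five imputations, 1,500 replicates, imputing on treatment and one baseline covariate. Imputed against true effect, in the table's row order: 51.7 vs 43.0, 50.9 vs 34.4, 50.5 vs 50.3, 50.6 vs 59.4 µm. The Monte Carlo standard error of the imputed mean is about 0.4 µm. The biases agree with the formula to within about 0.5 µm.

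**5. Do the planned analyses test this?** Under SAP Section 9.5.1 the Quade test and the COVID-19 analysis reuse the primary imputation. The OCT and completers sets (SAP Sections 6.2 and 6.3) require an observed follow-up FCT. None departs from missing at random.

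**The case against.** The strongest reply is that Section 8.2.1 is only permissive, while the instructions specific to this scan are emphatic. Section 8.1 itself presses for subjects to stay on study so that outcome data are collected. Section 7.6 answers non-compliance with re-education and names stopping treatment, not omitting scans, as the possible consequence. Section 7.1.7 sends disallowed therapy to the medical monitor. Sites may therefore rarely use these reasons. Placebo subjects may also seldom start a PCSK9 inhibitor, because Section 9.2.4 withholds lipid results and discourages outside lipid panels. All of this stands and limits the likely size. It does not remove the contradiction: Section 9.1.2 speaks of stopping drug and of late scans, not of disallowed therapy.

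Some stronger readings are tempting but unsupported:
- *The estimate is biased upward.* Non-compliance under Section 7.6 covers all study-required medication, so placebo subjects removed for poor statin adherence could push the other way.
- *The loss would go unnoticed.* Protocol Section 10.2.4 tabulates reasons for a missing final OCT, and SAP Section 9.2 summarizes exclusions from each analysis set. Tabulation shows the loss but does not correct it.
- *Every reason listed is an event the estimand includes.* Neither estimand names ineligibility or protocol deviation, and the PCSK9 clause is in the SAP alone.
- *Affected subjects leave the primary analysis.* Protocol Section 10.1 words it so for sample size, but the primary analysis imputes them.

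**Conclusion.** The contradiction is real: Sections 8.1 and 8.2.1 permit the primary-endpoint scan to be omitted for non-adherence or a disallowed therapy, while Section 9.1.2, the synopsis and the estimand call for it. The imputation cannot repair the loss and no planned analysis probes it.

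The consequence is a risk of informative missingness. It probably favours evolocumab, because non-adherence on evolocumab and PCSK9-inhibitor use on placebo both push that way. Size and sign are not determined. The working illustration, 50.97 µm reported against 45.9 µm true, assumes 10% of each arm affected, a shift of half the effect in each, and no affected subject scanned. A reader might take the span of about 5% to 25% (2.5/48.4 to 10.2/40.8) as an estimate of overstatement. It is not: it assumes equal shares in both arms, and its upper end has each affected subject gaining or losing the whole 50-week effect. If every final scan is obtained, bias from this source is zero under any assumption.

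**What to change.** Reconcile Protocol Sections 8.1 and 8.2.1 with Section 9.1.2 and the estimand. The result should be that events the estimand includes (non-adherence, and starting another lipid therapy, for which the SAP names a commercial PCSK9 inhibitor) are not by themselves grounds for omitting the already scheduled final OCT in consenting subjects. Both sections need attention, since changing 8.2.1 alone leaves the same list in 8.1. Which safety or clinical reasons justify omitting a catheter procedure is for the sponsor to settle, including how to treat subjects later found ineligible. The protocol and SAP estimands should also agree on the PCSK9 clause.

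In the SAP, add before unblinding one sensitivity analysis for subjects whose final OCT is missing for these reasons. It could be reference-based imputation, drawing off-drug evolocumab subjects from the placebo distribution and placebo subjects who started a PCSK9 inhibitor from the evolocumab distribution. A tipping-point analysis that shifts each arm separately would cover either sign of bias.

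Cost: a short amendment, a few scans already planned and one extra analysis. Scans not taken cannot be recovered later.

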8.2.2 Reasons for Removal From Study

Reasons for removal of a subject from the study are:

- Decision by sponsor
- Withdrawal of consent from study
- Death
- Lost to follow-up

8.3 Lost to Follow-up

A subject will be considered lost to follow-up if he or she repeatedly fails to return for scheduled visits and is unable to be contacted by the study site.

The following actions must be taken if a subject fails to return to the clinic for a required study visit:

- The site must attempt to contact the subject and reschedule the missed visit as soon as possible and counsel the subject on the importance of maintaining the assigned visit schedule and ascertain whether or not the subject wishes to and/or is able to continue in the study.
- In cases in which the subject is deemed lost to follow-up, the investigator or designee must make every effort to regain contact with the subject (where possible, 3 telephone calls and, if necessary, a certified letter to the subject's last known mailing address or local equivalent methods). These contact attempts are to be documented in the subject's medical record.
- If the subject continues to be unreachable, he/she will be considered to have withdrawn from the study with a primary reason of lost to follow-up.
- For subjects who are lost to follow-up, the investigator can search publicly available records [where permitted] to ascertain survival status. This ensures

that the data set(s) produced as an outcome of the study is/are as comprehensive as possible.

9. Study Assessments and Procedures

Study procedures and their time points are summarized in the Schedule of Activities (see [Table 2-1](#)).

As protocol waivers or exemptions are not allowed if an enrolled subject is subsequently determined to be ineligible for the study, this must be discussed with the sponsor immediately upon occurrence or awareness to determine if the subject is to continue or discontinue study treatment.

Adherence to the study design requirements, including those specified in the Schedule of Activities ([Table 2-1](#)), is essential and required for study conduct.

9.1 General Study Periods

This will be a multi-center, double-blind, randomized, placebo-controlled trial. The study consists of:

- Screening
- Double-blind treatment period
- EOS visit

Written informed consent must be obtained and will be implemented before protocol-specific procedures are carried out. The risks and benefits of participating in the study will be verbally explained to each potential subject prior to entering the study. The procedures to be performed during the study are described below and are summarized in the Schedule of Activities ([Table 2-1](#)).

9.1.1 Screening, Enrollment and/or Randomization

Informed consent must be obtained before completing any screening procedure or discontinuation of standard therapy for any disallowed therapy. After the subject has signed the informed consent form, the site will register the subject in the IVRS/IWRS and screen the subject in order to assess eligibility for participation. The screening window is up to 1 week.

All screening evaluations must be completed and reviewed to confirm that potential subjects meet all eligibility criteria, including acceptability of OCT data set as determined by the imaging core laboratory. The investigator will maintain a screening log to record details of all subjects screened and to confirm eligibility or record reasons for screening failure, as applicable.

If a subject has not met all eligibility criteria at the time of randomization, the subject will be registered as a screen fail IVRS/IWRS. Subjects cannot undergo rescreening during the same admission, (ie, index date [admission]). Rescreening is only permitted if a subject is re-admitted for new occurrence of NSTE-ACS that is not related to the NSTE-ACS at index admission. Screen fail subjects may be eligible for rescreening 2 times.

All rescreened subjects must consent. Rescreen subjects must be registered as rescreens in IVRS/IWRS. Once the subject is registered as rescreened, a new 7-day screening window will begin. With the exception of the screening placebo injection, rescreened subjects will repeat all screening procedures. Rescreened subjects will maintain the originally assigned subject identification number.

For procedures regarding LDL-C assessments during screening, these should occur between admission for NSTE-ACS and the coronary angiogram. Subject eligibility ([Section 6.1](#); inclusion criterion [104](#)) based on subjects' statin dose at the time of LDL-C blood sample measurement is as follows:

No statin use

- LDL-C: ≥ 130 mg/dL

Low- or Moderate-intensity statin dose (see [Table 7-1](#))

- LDL-C: ≥ 80 mg/dL

High-intensity statin dose (see [Table 7-1](#))

- LDL-C: ≥ 60 mg/dL

Day 1 of the treatment period (ie, first dose of investigational product) must happen within 7 days of the signing of the informed consent.

9.1.2 Treatment Period

Visits will occur per the Schedule of Activities ([Table 2-1](#)). On-study visits may be completed within 50 weeks and must occur within ± 7 days of their specified date (with the exception of the week 50 OCT and IVUS). The date of the first dose of investigational product is defined as day 1. All subsequent doses and study visits will be scheduled based on the day 1 date. Administration of investigational product is to be administered last during each visit that it is required.

Approved

Before each study visit where fasting lipid samples are obtained, subjects must be fasting overnight. If the subject is not fasting for the day 1 visit, no visit procedures are performed and the visit should be rescheduled within the applicable protocol windows. If subject is not fasting after day 1, all procedures except fasting labs and investigational product administration, if applicable, will be performed and another visit should be scheduled, within the visit window if possible, for fasting labs and investigational product administration.

The study includes collection of biomarker samples.

Final, follow-up OCT and IVUS should take place 50 ± 2 weeks (ie, 48 to 52 weeks) after initial baseline image acquisition. It is critical that the follow-up OCT and IVUS be obtained for all subjects, regardless of whether they discontinued study drug prematurely or are outside the 50 ± 2 weeks window.

9.1.2.1 Clinically Indicated Catherization Prior to Week 40

For subjects requiring coronary angiography prior to week 40, the final OCT and IVUS examination should not be performed in these subjects at the time of clinically indicated catherization. Subjects will remain on study drug and complete all required visits and procedures, including the week 50 OCT and IVUS.

For subjects requiring coronary angiography with intervention of the targeted vessel prior to week 40, these subjects will continue investigational product and complete all study visits and procedures with the exception of the week 50 OCT and IVUS.

9.1.2.2 Clinically Indicated Catherization at Week 40 Prior to Week 50

Any subjects who require cardiac catherization for clinically indicated reasons at week 40 or later must have OCT and IVUS examination of the target vessel performed at that time. The week 50 OCT and IVUS will not be required for these subjects. If PCI of a non-target vessel is required, subjects will undergo the final OCT and IVUS after PCI is completed. If PCI of the target vessel is required, the final OCT and IVUS should be completed prior to PCI if clinically appropriate. These subjects will continue investigational product and complete all study visits and procedures with the exception of the week 50 OCT and IVUS.

